6.1.2. Processing of Breath Samples

Breath collection bags will be immediately sealed following collection and labeled with the subject number and collection time point until processed. Breath samples will be centrally processed, and resulting levels will be recorded in the subject CRF.

The breath testing will be performed by Metabolic Solutions, a CLIA accredited laboratory (CLIA ID #30D0970292) at their facility in Nashua, NH. Breath samples from each study subject will be labeled with the de-identified study subject ID, the date and time of collection, and a study ID. The breath samples from a study subject will be shipped overnight via FedEx in an approved and appropriately labeled shipping container. One container is used for each subject and will hold the 300 ml breath bags collected from the subject. Metabolic Solutions will measure the CO₂ concentrations in each bag and also the ¹³CO₂ change over baseline for the post-nebulization breath bags. They will also properly dispose of the breath bags after measurement. The Metabolic Solutions measurements will be tied to the de-identified study

subject ID and collection date/time in the subsequent report sent to the PI for entry into the subject's case report form.

6.1.3. Processing of samples for microbiome analysis

A oropharyngeal swab and a portion of the collected sputum sample will be preserved with a nucleic acid protectant that also neutralizes infectious organisms, such as Zymo Biosciences DNA/RNA shield or equivalent. We will conduct microbial sequencing to determine the presence of microorganisms and their relative abundance. To this end, total nucleic acid (DNA and/or RNA) will be isolated to allow for microbiome analysis by sequencing. Microbiome sequencing will be done at UNM laboratories under direct supervision of the study investigators. Sequencing will be conducted on a next generation sequencing system, such as the Illumina MiSeq sequencer. The microbiome content will be determined through bioinformatic analysis of the sequencing reads with a taxonomic database such as the Greengenes Consortium Database, Kraken database or a similar microbiome classification database. These samples will be labeled with the de-identified study subject ID, the date and time of collection, and a study ID. Raw sequence data generated from the sequencer in the format of a .fastq file and labeled only with the study number and no identifying data may be transferred, stored, and analyzed using web and/or cloud-based solutions.

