5.6. Blinding and Unblinding of Study Medications

All study participants will receive ^{13}C -urea, no blinding or dummy doses will be utilized in this study.

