9.2. Study Endpoints

9.2.1. Efficacy Endpoints

Efficacy endpoints will include the following:

- Evaluate the exhaled ¹³CO₂ levels at each time point post-nebulization
- Evaluate the relationship between the exhaled ¹³CO₂ levels at each time point and subject's causative pathogen based upon sputum culture or NGS analysis
- Evaluate the sensitivity and specificity of the ¹³C-urea breath test for urease producing pathogens
- Evaluate the positive and negative predictive value of the ¹³C-urea breath test for urease producing pathogens
- Correlation of the ¹³C-urea breath test with CURB65 in subjects with sputum cultures or NGS results positive for urease pathogens
- Correlation of the ¹³C-urea breath test with PSI in patients with sputum cultures or NGS results positive for urease pathogens
- Univariate association of all study variables with urease pathogen caused pneumonia
- Multi-variate logistic regression model for urease pathogen caused pneumonia utilizing study variables that are significant in univariate analysis to compute odds ratio for each model variable and overall explanation of variance by model

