10.6. Provision of Study Results and Information to Investigators

The investigator and study staff will have access to the research results and will be able to link the results to a particular subject. The investigator and study staff will be directed to hold this information confidentially.

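### For the endpoints that accept sputum culture or NGS, nothing keeps the urease-pathogen call blind to the breath result, and no calling rule limits the judgement involved

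*Combined protocol and SAP*

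**What the plan says.** **Breath result.** An external laboratory measures the bags. Section 6.1.2 ties its measurements to the "subject ID and collection date/time in the subsequent report sent to the PI for entry into the subject's case report form".

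**Sequencing.** Section 6.1.3: "Microbiome sequencing will be done at UNM laboratories under direct supervision of the study investigators". The output is which organisms are present and in what relative abundance, and the taxonomic database is left open. On labelling: "These samples will be labeled with the de-identified study subject ID, the date and time of collection, and a study ID". The breath bags carry the same subject ID.

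**Access.** Section 10.6: "The investigator and study staff will have access to the research results and will be able to link the results to a particular subject". The next sentence asks staff to keep this information confidential. Section 10.1.4 describes one spreadsheet, open to approved study staff.

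**Reference standard.** Section 9.2.1 relates exhaled ¹³CO₂ to the "causative pathogen based upon sputum culture or NGS analysis". The Synopsis efficacy analysis also compares breath positive/negative calls with culture or NGS. The primary objective (Section 2), the rationale (Section 3.2) and Section 9.5 refer to sputum culture alone. The bullets on sensitivity, specificity and predictive values in Section 9.2.1 name no reference test.

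**Masking.** Section 5.6, on study medication, states that "no blinding or dummy doses will be utilized in this study". Section 10.4 mentions blinded data among the closure conditions, but no procedure creates any. No section covers masking of the people who read either test.

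**The concern.** Accuracy estimates mean what they appear to mean only if each test is read without knowledge of the other. With mixed flora, or when culture and NGS disagree, naming a causative organism takes judgement. A reader who knows the breath result may settle such cases in its favour. That is review bias, and it flatters the breath test.

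The study tests no formal hypothesis (Section 9.3.2), so no type I error is at stake. The accuracy estimates are the product, however: Section 9.1 says the findings will be used to size a later, adequately powered study. Accuracy carried forward too high would tend to make that study too small.

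**Working it through.** The plan states no accuracy, precision or power figure, so there is none to reproduce. The check has four steps.

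**1. Who can see what.** Breath results reach the PI by subject ID (6.1.2). Study investigators supervise the sequencing (6.1.3). The investigator and staff can link results to subjects (10.6). A shared de-identified subject ID protects privacy but does not mask one result from the other. Nothing in 6.1.2, 6.1.3, 9.5 or 10.6 sets an order of release or restricts access.

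**2. Is there room for judgement?** On the reference side there is no list of urease-positive taxa, no abundance threshold and no rule for culture-NGS disagreement. On the breath side the ¹³CO₂ value is an instrument reading from an outside laboratory. What stays open there is the cut-off, which is not given, and the sampling time, which Section 9.5 chooses by how well ¹³CO₂ predicts the pathogen.

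**3. Direction.** Let *a* false negatives be re-labelled as true negatives and *b* false positives as true positives.

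- Sensitivity = (TP + b) / (TP + FN + b − a)
- Specificity = (TN + a) / (TN + FP + a − b)

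The odds are (TP + b)/(FN − a) and (TN + a)/(FP − b). Both rise whenever *a* or *b* is positive, so sensitivity and specificity increase together.

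**4. Size, on assumed counts.** Sputum is required only in Cohort B (Appendix A, Table 1), which has at most 75 − 15 = 60 subjects. Assume 12 are truly positive and 48 negative, with TP = 10, FN = 2, TN = 43 and FP = 5. That gives 2 + 5 = 7 discordant subjects.

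| Re-labelled | Share of discordant | Sensitivity | Specificity |
|---|---|---|---|
| none | 0/7 | 10/12 = 83.3% | 43/48 = 89.6% |
| 1 FN, 1 FP | 2/7 = 29% | 11/12 = 91.7% | 44/48 = 91.7% |
| 2 FN, 3 FP | 5/7 = 71% | 13/13 = 100% | 45/47 = 95.7% |

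The last row removes every false negative, so it is near the extreme.

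A second set of assumptions gives a range. Take prevalence of 15%, 25% or 35% (9, 15 or 21 positives among 60) and re-label three subjects each way. The denominators do not change, so sensitivity rises by 3/9 = 33, 3/15 = 20 or 3/21 = 14 points. Specificity rises by 3/51 = 5.9, 3/45 = 6.7 or 3/39 = 7.7 points. If only three false positives move, starting from 10/15 and 36/45, the result is 13/18 = 72% (from 67%) and 36/42 = 86% (from 80%).

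**The case against.** The strongest reply has five parts.

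- **The primary comparison is with culture.** Sputum is sent for culture (6.1.1) or comes from the ED workup (3.1), and no section has the investigators read it. A reader might infer that the trial's headline accuracy is inflated. The documents do not support that; the exposure lies in the comparisons that admit NGS. This part stands.
- **Supervising sequencing is not adjudicating a pathogen.** A reader might infer that the same people receive the breath results and make the call. Section 6.1.2 names the PI, Section 6.1.3 the study investigators, and no section assigns the call to anyone. Nor is it stated which result arrives first. This also stands. What remains is that access is open to study staff generally, so the gap exists whoever makes the call.
- **Section 5.6 concerns medication in a single-arm study.** It cannot be read as a decision to leave test readers unmasked. The finding rests on the absence of any provision for test readers.
- **The root problem is the undefined call.** With a fixed rule, little judgement is left to bias. This is right, and the fix begins there. Likewise, a breath cut-off cannot be applied blind when the plan has none.
- **The illustration is assumed, and sampling error is large.** The exact 95% interval for 10/12 is about 52% to 98%. True, but sampling error does not favour one direction, whereas re-labelling toward the breath result always does.

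**Conclusion.** The gap is real but narrower than it first appears. For the endpoints that accept culture or NGS, nothing keeps the pathogen call independent of the breath result, and no calling rule limits discretion. Any settling of discordant cases toward the breath result raises both accuracy measures. The culture-only comparison is much less exposed, and the external ¹³CO₂ measurement itself is not in question.

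The documents show an opportunity for bias; they do not show that bias will occur, nor how large it would be. In the 12/48 illustration, re-labelling two subjects adds 8 points to sensitivity and 2 to specificity; re-labelling five adds 17 and 6. Prevalence, accuracy and the number of ambiguous cases are all assumptions. In a descriptive Phase 1 study the consequence falls on the estimates carried into the next study's sample size. That is enough to justify a cheap change.

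**What to change.** In Sections 6.1.2, 6.1.3 and 10.6:

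1. Write the calling rule beforehand: which taxa count as urease-positive, what NGS abundance counts, and how culture and NGS rank when they disagree.
2. Have existing staff assign each subject's urease status under that rule and lock it before breath results are released to them.

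In the analysis sections:

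3. Report culture-only accuracy alongside culture-or-NGS accuracy. This also deals with the difference between Section 9.5 and the Synopsis.
4. Fix any breath cut-off before breath results are linked to pathogen status. Where the cut-off or sampling time is chosen from these data, label the resulting accuracy as exploratory.

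**Cost.** A written rule, a lock step, and a change in release order and access rights; no new staff. The downside is that breath results reach the PI and the CRF later. Section 10.1.4 asks for contemporaneous CRFs and Appendix E (4.9) for full source verification; neither rules out a short delay. Subjects are treated by standard institutional practice (3.1), and the safety review form (Appendix C.1) has no field for the breath result. This is a cheap improvement.

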6.2. Demographic and Baseline Characteristics Assessment

6.2.1. Demographics

Demographics information will be collected during screening visit including age, sex, ethnicity, race, weight, height, BMI. CURB-65 Pneumonia Severity Score, and/or Community-Acquired Pneumonia Severity Index (PSI) may be determined when required data are available.

6.2.2. Medical History

The investigator or designee will document each subject's medical history during the screening visit. Documentation of medical history should report tobacco use and diagnostic criteria for healthcare associated pneumonia, including hospitalization within 90 days, residence in nursing home or long term care facility, recent visit to hospital or hemodialysis unit, or receipt of IV antibiotics, chemotherapy or wound care within 30 days. When available ED diagnostic chest x-ray should be reported in the medical history and included in the subject file.

6.2.3. Clinical Laboratory Tests

The investigator or designee will document results of laboratory tests collected in the course of routine care during the subject's hospitalization. These results will be collected on the CRF.

6.2.4. Physical Examination

The investigator or designee will perform a physical examination (HEENT, cardiovascular, respiratory, gastrointestinal, neurological, dermatologic, and musculoskeletal systems) during the screening visit. The oral cavity should be examined for evidence of oral infection (i.e. abscess) as part of the physical examinations (examination by a dentist is not required).

The Principal Investigator may perform a physical examination (the extent of which is determined by the study investigator) at any time during the study if indicated by change in a subject's medical condition.

6.3. Safety Assessments Description

6.3.1. Clinical Laboratory Tests

During screening, subjects will have samples collected for testing as follows:

Sputum:

- Bacterial culture (only required for Cohort B)

Urine

- Pregnancy test (female subjects)

Laboratory tests do not need to be repeated if samples have already been collected as part of the presenting or admission workup for the current ED visit or hospitalization.

6.3.2. Vital Sign Measurements

Resting vital signs will include resting blood pressure, resting pulse, respiratory rate, peripheral oxygen saturation, and temperature; temperature will only be required for vital signs collected for screening. Resting tests must be obtained after resting (seated/supine) for ≥ 5 minutes.

Vital signs including blood pressure, heart rate, respiratory rate and peripheral oxygen saturation will be recorded prior to nebulization, and following completion of sample collection. Subjects will have continuous pulse oximetry monitoring during sample collection and urea nebulization, and any change in oxygen requirement will be recorded.

Actual times will be recorded in the subject CRF.

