3. INVESTIGATIONAL PLAN

3.1. Overall Study Design

This is a Phase 1, open-label evaluation of an inhaled ¹³C-urea breath test in the identification of urease positive bacteria in patients diagnosed with pneumonia in the emergency department (ED). This study will enroll up to 75 adult male and female subjects at two US sites in two cohorts.

Adult subjects will be screened for participation in two dosing cohorts to be enrolled sequentially. Cohort A will enroll 15 subjects presenting to the study sites with pneumonia symptomatology that is planned for outpatient treatment. Following enrollment and review of the safety of dosing in Cohort A, subjects receiving a diagnosis of pneumonia in the ED that are planned for admission will be screened for enrollment in Cohort B. Eligible subjects will provide informed consent, medical history, and samples for laboratory testing (including pregnancy testing for females of childbearing potential) during screening. Subjects will be evaluated for their CURB-65 Pneumonia Severity Score, and Community-Acquired Pneumonia Severity Index (PSI) where required data are available.

Prior to breath test administration, Cohort B subjects will provide a sputum sample for bacterial culture; sample may be induced, or collected as part of initial ED workup if appropriate culture has been ordered. Subjects will undergo breath test with collection of baseline breath samples (up to 6), followed by complete nebulization of ¹³C-urea solution. Immediately following the end of nebulization, breath collection bag samples will be collected at up to 6 time points with at least 1 minute intervals within 10 minutes post-nebulization. Exhaled breath bags will be centrally processed to determine the change in exhaled ¹³CO₂ levels. Vital signs, including resting blood pressure, resting pulse, respiratory rate, peripheral oxygen saturation, and temperature will be collected prior to, and following completion of, nebulization treatment. In the event of bronchospasm, during or following nebulization, albuterol rescue will be available for treatment at the discretion of the investigator.

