After administration of nebulized ¹³C-urea solution, subjects will be monitored at the study site for any adverse events. Adverse events directly related to nebulizer administration would be expected to present within minutes of nebulization. Evidence shows that, generally, symptoms of anaphylaxis appear between 1-15 minutes after exposure to an agent. Symptoms of anaphylaxis may present as lightheadedness, dizziness, difficulty breathing, wheezing, hives, swelling under the skin, rashes, and/or nausea. The study team will monitor subjects for 20 minutes after nebulization for any adverse events. All subjects will receive standard care in the hospital setting prior to and after completion of study procedures. Subjects will sign and be given a copy of the consent form which has contact information and instructions that they should return to the emergency department if they suspect they are suffering from any symptoms related to the nebulization. The instructions in the consent form also specify that, if returning to the emergency department at the corresponding study site with symptoms they believe are due to the study, they should bring the consent form with them to the ED and ask that the study site Principal Investigator be immediately called and notified on their return. In Cohort A, all safety observations prior to discharge, and in Cohort B the clinical course over the hospital admission,

will be reviewed and submitted to the safety monitoring committee as described below in Sections 7 and 8.

Once required tests are complete, the subject will be treated/followed according to standard institutional protocol/practice. The subjects' clinical course will be followed for at least 24 hours, where possible, to document the final diagnosis and outcome.

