4.3.2. Replacement of Subjects

Subjects who do not complete ¹³C-urea nebulization and all scheduled breath sample collection time points may be replaced in this study.

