5. TREATMENTS

5.1. Administration of Study Medication

Administration of ^{13}C -urea solution will be completed using an Aerogen Aeroneb Solo nebulizer device, within 60 minutes following reconstitution with 3 mL of sterile water for injection. The solution will be nebulized until the full dose has been administered, with subjects breathing normally through their mouths using the nebulizer mouthpiece. The start and stop time of nebulization will be recorded in the subject CRF. The time nebulization is completed or discontinued will be considered Time 0 for post-dose breath sample collection.

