6.1. Efficacy Assessments

6.1.1. Sample Collection

Baseline breath collection will be completed within 30 minutes prior to nebulization using up to six breath collection bags. Sufficient exhaled breaths to fill the bag will be collected at each defined time point. Breath collection will be by direct exhalation into a bag, or by a breath capture device attached to the nebulizer.

Up to six post-nebulization breath samples will be collected within 10 minutes after completing the nebulized dose, at intervals of 1 minute or greater. Breath collection will be by direct exhalation into a bag, or by a breath capture device attached to the nebulizer.

Samples will be collected within ± 1 minute of the scheduled post-dose time. Actual times will be recorded for all samples as the time of first collected exhaled breath.

Sputum samples will be collected by trained study personnel per standard clinical practice within 15 minutes of the breath test. In brief, subjects will be asked to take several deep breaths and then produce a forceful cough. The subject will be encouraged to expectorate into a sample cup, and the sputum sample will be sent for culture. If the subject has difficulty producing a sputum sample, nebulized saline may be used to loosen secretions and encourage sputum production.

A oropharyngeal swab will be collected per standard clinical practice, and the sample will be preserved for microbiome analysis. A portion of the collected sputum sample will be preserved for microbiome analysis.

Sample collection will be performed according to GCP in a room in the emergency department or Clinical and Translational Sciences Center (adjacent to UNM-ED, Cohort A only).

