9.3. General Considerations for Statistical Analysis

9.3.1. Analysis Datasets

Intent-to-Treat (ITT) Analysis Set: The ITT set will include all subjects who receive nebulized ¹³C-urea. The ITT set is also referenced as the Safety analysis set. All safety analysis will be based on the ITT analysis set.

Modified Intent-to-Treat (mITT) Analysis Set: The mITT subjects include all ITT subjects who provide at least one post-dose breath sample. The mITT analysis set will be used for efficacy analysis.

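### Required continuous oximetry stops when breath sampling stops, so about 9 to 15 of the 20 observation minutes have none, and no vital-sign set is due at minute 20

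*Combined protocol and SAP*

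**What the plan says.** Section 3.1 sets the observation period: "The study team will monitor subjects for 20 minutes after nebulization for any adverse events". It attaches no instrument to that period. Its own vital-sign rule is that a set, including saturation, "will be collected prior to, and following completion of, nebulization treatment".

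Section 6.3.2 says what is measured and when. Oximetry: "Subjects will have continuous pulse oximetry monitoring during sample collection and urea nebulization, and any change in oxygen requirement will be recorded". Blood pressure, heart rate, respiratory rate and saturation "will be recorded prior to nebulization, and following completion of sample collection". Actual times go on the case report form, but no target minute is given. Resting measurements need at least 5 minutes of rest first.

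Section 6.1.1 fixes the sampling window: up to six post-dose samples "within 10 minutes after completing the nebulized dose, at intervals of 1 minute or greater", with a tolerance of 1 minute either way. Section 3.1 has sampling begin as soon as nebulization ends. Section 5.1 sets the clock: "The time nebulization is completed or discontinued will be considered Time 0 for post-dose breath sample collection".

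In Appendix A, Table 1, the last column with vital signs is 0 to 10 minutes after nebulization. Adverse event monitoring is listed in Section 6.4.2 and Table 1, and Section 7.1 runs it to about 2 hours after dosing.

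The plan allows for subjects who stop early. Under Section 4.3.2, those who do not complete nebulization and "all scheduled breath sample collection time points may be replaced in this study". Section 9.3.1 keeps dosed subjects without a post-dose sample out of the efficacy set: "The mITT subjects include all ITT subjects who provide at least one post-dose breath sample". Section 4.3.1 asks for an investigator evaluation of subjects who leave the study early, before they leave the hospital.

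**The concern.** A safety measurement has been tied to an efficacy procedure. The plan chose 20 minutes as the period for watching the subject, but the probe may come off when the last bag is filled. A site that removes it at minute 5 complies fully. The number of samples is a ceiling, so fewer samples mean an earlier end, and a subject who tolerates the test poorly may have the shortest required oximetry.

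Safety and tolerability is a stated objective (Section 2), and the medical monitor's review of the 15 Cohort A subjects decides whether admitted patients may be dosed (Section 6.6). Section 6.4.1 recruits from patients who may already be short of breath or have COPD, and Section 4.2 does not exclude COPD. In such patients a symptom alone is a weaker sign of a fall in saturation. Section 6.1.1 also lets Cohort A sampling take place in a research center next to the emergency department, so routine bedside monitoring cannot be assumed to fill the gap. A late change that is neither noticed nor measured does not reach the medical monitor.

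**Working it through.** The plan gives no figure for time without oximetry, so there is none to reproduce. Its one relevant figure is the 20-minute observation in Section 3.1. The rest is timeline arithmetic.

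**Inputs**
- Observation: 20 minutes after nebulization (Section 3.1).
- Time 0: nebulization completed or discontinued (Section 5.1).
- Post-dose samples: at most 6, starting at about minute 0 (Section 3.1), at least 1 minute apart, within 10 minutes, tolerance 1 minute (Section 6.1.1).
- Continuous oximetry after Time 0: until sampling ends (Section 6.3.2).

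**Formulas.** Let S be the minutes from Time 0 to the end of sampling. Minutes without required continuous oximetry = 20 − S. The earliest S with n samples is (n − 1) × 1. The latest is 10 + 1 = 11.

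| Case | S | 20 − S | Share of 20 min |
|---|---|---|---|
| Six samples, 10-minute limit plus tolerance | 11 | 9 | 45% |
| Six samples, last at the 10-minute limit | 10 | 10 | 50% |
| Six samples, 1 minute apart from Time 0 | 5 | 15 | 75% |
| Four samples, 1 minute apart | 3 | 17 | 85% |
| Three samples, 1 minute apart | 2 | 18 | 90% |
| No post-dose sample | 0 | 20 | 100% |

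The first three rows are the main result. The last three are corner cases. If the tolerance is also applied to a sixth sample scheduled at minute 5, S is 4 and the remainder 16. Against that, a sample's time is its first collected breath, so sampling really ends slightly later than S.

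**The one later vital-sign set.** With six samples it can be taken from minute S = 5 to 11. If the 5-minute rest is counted after sampling, it can be taken from S + 5 = 10 to 16. At these earliest times it falls between 20 − 16 = 4 and 20 − 5 = 15 minutes before observation ends. If the Table 1 column binds, the set is done by minute 10 and minutes 10 to 20 have none. On every reading, no set is required at minute 20.

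**Subjects with no post-dose sample.** Required oximetry ends with nebulization. The Section 6.3.2 set is timed from the end of sampling, which does not occur. What remains is the untimed set in Section 3.1, the Table 1 entry at 0 to 10 minutes, and the Section 4.3.1 evaluation, which sets neither a minute nor oximetry.

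**Cost of covering the rest (six samples, 75 subjects).** 75 × 9 = 675 minutes (11.25 hours) to 75 × 15 = 1,125 minutes (18.75 hours) of probe time.

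**The case against.** The strongest reply is that nothing here is inconsistent. Section 3.1 promises observation for adverse events, Section 6.3.2 says which instruments are used and when, and neither rule breaks the other. The plan also has a reason for measuring early: Section 3.1 expects events caused directly by the nebulizer in the first few minutes, and oximetry covers all of nebulization plus the sampling that follows. More than 100 people have received the product without a serious adverse event (Section 8.4), and acute asthma exacerbation is excluded (Section 4.2). The safety endpoints are adverse events and death, ICU transfer or intubation (Section 9.2.2), and Section 9.6 plans no summary of saturation or vital signs. A minute-20 reading would therefore count mainly if it led to an adverse event, and that route is already open. Finally, finding the best sampling time is an objective, which favors spreading samples over the window and a gap nearer 10 minutes than 15.

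Most of this stands, and it limits the point to a modest improvement. It does not remove it. Earlier exposure was in healthy volunteers, cystic fibrosis patients and TB-screening subjects (Sections 1 and 5.4); tolerability in emergency-department pneumonia is what this study sets out to learn. A single reading, possible at minute 5, does not cover the following 15 minutes.

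A reader might infer three stronger things that the documents do not support:
- That subjects are unmonitored after sampling, or that anaphylaxis would be missed. Section 3.1 gives onset at 1 to 15 minutes, lists symptoms that staff or subject would notice, and keeps staff watching to minute 20.
- That early stoppers are left with nothing. Section 4.3.1 requires an investigator evaluation, and Table 1 lists vital signs at 0 to 10 minutes whether or not samples are taken.
- That gaps of 17 to 20 minutes are to be expected. The plan permits them but does not suggest they will be common.

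**Conclusion.** The point holds as a low-cost improvement to a design choice, not as a contradiction in the plan. With six samples, 9 to 15 of the 20 observation minutes have no required continuous oximetry, and about 10 if sampling fills its window. Those minutes contain at most one required vital-sign set, at no scheduled time, with none due at minute 20. This applies to up to 75 subjects, including the 15 whose review opens Cohort B.

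The figures are shares of observation time, not of risk. What is lost is objective detection of late changes in saturation or vital signs that neither staff nor subject notices; the documents give no rate for such changes.

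The conclusion assumes that sampling starts at about Time 0, that the tolerance may extend the last sample to minute 11, and that the post-dose sets described in Sections 3.1 and 6.3.2 and in Table 1 are one and the same. The value of about 10 further assumes spread-out sampling, which the plan does not fix.

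**What to change.** In Section 6.3.2, continue pulse oximetry and the recording of changes in oxygen requirement until 20 minutes after Time 0, with Time 0 as in Section 5.1 and whether or not breath samples are collected. Move the post-sampling set of blood pressure, heart rate, respiratory rate and saturation to minute 20, or keep it and add a timed set there. List the 20-minute observation in Section 6.4.2 and add a 20-minute column to Appendix A, Table 1.

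The cost is a short amendment, one case report form time point and, with six samples, about 9 to 15 more probe minutes per subject (about 11 to 19 hours over 75 subjects). Staff must already be watching during those minutes. Moving the existing set adds no measurement; adding one adds a single set per subject. The downside is that some low readings will come from the pneumonia itself, with no control group to separate them. The pre-dose set gives each subject a comparison but does not remove that ambiguity.
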